4.5. CENTRE

Royal Prince Alfred Hospital

5. STUDY PARTICIPANTS

5.1. INCLUSION CRITERIA

Inclusion Criteria:

Elective non-cardiac, non-intracranial surgery

Requiring at least a 2-day stay in the hospital

Age >60 years old

Sex: Females and Males

Willingness to Provide informed consent and participate and comply with study requirements

English speaking to permit informed consent, cognitive and delirium assessments.

5.2. EXCLUSION CRITERIA

Exclusion Criteria:

Non-english speaking

Participants who may have received an investigational new drug within the last 7 days/weeks.

Participants who lack capacity to provide informed consent.

Participants with prior known intolerance/allergy to SSRIs or fluvoxamine

[figure not shown]
Planned postoperative ventilation

Patients on medications that interact with fluvoxamine: hepatic metabolism by CYP1A2 (theophylline, clozapine, tizadine, olanzapine), metabolism inhibited by fluvoxamine (diazepam, alprazolam, phenytoin), sigma-1

agonists/antagonists (donepezil, sertraline), risk of serotonin syndrome (St John’s Wort, selective serotonin reuptake inhibitors (SSRIs), tricyclic antidepressants (TCAs)

6. STUDY PROCEDURES

6.1. STUDY FLOW CHART

Forty-six surgical patients will be randomized 1:1 to a prospective interventional parallel arm double-blinded placebo-controlled trial. All patients will undergo baseline cognitive screening, 3D-CAM assessment, and DRS-R-98 scoring at the enrolment visit. The intervention arm will receive five doses of oral fluvoxamine capsules, 100mg the night before surgery, 100mg twice daily on the day of surgery and on POD 1; pharmacokinetic modeling predicts high sigma-1 receptor binding at POD 1-2, coinciding with anticipated peak delirium incidence.³⁰ A placebo capsule will be administered at the same schedule for those in the control arm.

Outcome measures include: (1) Feasibility: Incidence and reasons for screen failures and withdrawals, (2) Safety/feasibility: incidence/severity/relatedness of adverse events, number/reasons of missed study drug administrations, (3) Feasibility: Incidence and reasons for missed outcome measurements, (4) Feasibility: Delirium incidence/severity (3D-CAM-S) at enrollment, POD 1-4 (both AM and PM), (5) Feasibility: IL-8 and NfL on POD 1 AM and POD 2 AM, and (6) Feasibility: awake EEG SWA on POD 1 AM and POD 2 AM.

6.2. INVESTIGATION PLAN

6.2.1. METHODOLOGY

Interventions	Enrolment Visit	Visit 1 (Intraop)	Visit 2 (PM day of surgery)	Visit 3 (POD1)	Visit 4 (POD2)	Visit 5 (POD3)	Visit 6 (POD4)	Visit 7 (POD 30)
Participant Consent	✓							
Inclusion / Exclusion criteria	✓							
Physical examination	✓			✓				
Cognitive screen [#]	✓						✓	✓
Adverse Event & Serious Adverse Event Assessment				✓	✓	✓		
Delirium Rating Scale-Revised-98 ^{&}	✓		✓	✓	✓	✓	✓	
Richmond Agitation/Sedation Scale & VAS (pain) [^]	✓		✓	✓	✓	✓	✓	
EEG monitoring [*]				✓				
3D-Confusion Assessment Method - S ^{&}	✓		✓	✓	✓	✓	✓	
Satisfaction Questionnaire [^]							✓	
Blood sample collection		✓		✓	✓			
C-Reactive Protein, Troponin, White cell count ⁺		✓		✓	✓	✓	✓	

[#]^{*}[&][^] Not SOC

[#]The preoperative cognitive screen will include the modified telephone interview of cognitive status (TICS-M) and verbal fluency and completion of the WHO Disability Assessment Schedule (WHODAS) and Geriatric Depression Scale 15 (GDS15). Total time will be approximately 25 minutes.

&The 3D-CAM-S and DRS98 are questionnaires that allow for accurate diagnosis of delirium. These are conducted twice daily postoperatively (between 6.00 to 10.00 and 16.00 to 20.00).

NOTE: average score or worst score be used for analysis

^If Patient RASS score low/unable to conduct a delirium assessment – data missing or re-assessed within 2 hours.

*Visit 3 EEG collection will include a 256 electrode compumedics EEG will conducted on postoperative days 1 or 2 (if patient is comatose on POD1 it will be deferred to POD2) by trained research staff using a saline cap. The recording will last 40 minutes

+Blood samples for CRP, Troponin and WCC will be collected when feasible from pre-existing access lines and during routine blood collection to minimise invasive procedures and risk of infection. Blood samples will be collected by accredited members of the research team or ward/ICU staff.

6.2.2 ADVERSE EVENTS/SERIOUS ADVERSE EVENTS

Rates of nausea, diarrhea, headache, and insomnia will be evaluated from evening before surgery through POD 3 for individuals in both the intervention and control arms. These rates will be tabulated for all events, with consideration of severity and potential relatedness to fluvoxamine or drug-drug interactions.

6.3. STUDY PROCEDURE RISKS

Fluvoxamine has been associated with nausea, vomiting, drowsiness, dizziness, loss of appetite, insomnia, weakness, bruising, tremors and sweating. Anaesthetic doctors will be contacted prior to surgery to inform them of patient participation, they will be informed of an increased risk of nausea and vomiting in order to administer prophylactic antiemetics if required.

SSRIs are considered safe in the perioperative period and are continued perioperatively. SSRIs have been associated with increased bleeding risk, largely based on theoretical actions of serotonin on platelets, however this is not considered a clinical problem³¹. We will report blood loss to the DSMB after every 10 patients randomized.

The following risks are deemed very rare:

Small risk of serotonin syndrome if fluvoxamine is co-administered with other strongly serotonergic medications e.g. SSRIs, MAOIs, TCAs, tramadol, triptans etc.

Small risk of clinically relevant pharmacokinetic interactions through CYP1A2 e.g. increasing levels of warfarin, phenytoin, carbamazepine, reducing level of clopidogrel

Very small risk of inducing hyponatraemia in vulnerable elders (if required post-operation sodium levels will be monitored)

All risks will be outlined in the Patient Information and Consent Sheet and discussed during the consent process. All patient medications will be screened prior to enrolment in study and participants will be asked to list their current medications.

6.4. PARTICIPANT RECRUITMENT AND SCREENING

Non-cardiac, non-intracranial surgical patients at Royal Prince Alfred Hospital and Washington University will be recruited who are aged over 60 years old. Screening and recruitment will take place through the pre-admission clinic in conjunction with the anaesthetic assessment. All screening, recruitment and study activities including the pre-procedural interventions will be managed by anaesthetic research staff and anaesthetic doctors prior to and on the day of surgery.

If a patient displays cognitive dysfunction during pre-operative screening and enrolment, they will not meet eligibility criteria and will not be enrolled in trial. Based on patient pre-operative history this may be reported to the PI and if required discussed with treating team.

Will participants be screened?	Yes
If yes, what data will be collected? (NB, if participant is not eligible, will data collected be destroyed or kept?) This should be mentioned in PIS/CF)	Patients will be screened via the theatre lists to determine eligibility based on type of procedure and age. ASA status will be determined for eligibility at this time. Screening logs will not be collected.
Who will make initial contact with participants?	The initial contact with the patient will be made by a member of the anaesthetic department in the pre-admission clinic. Following this the anaesthetic doctor or a member of the research team will contact the patient to discuss involvement in the trial.
Who will perform the consent process? How will this be carried out?	Prior to obtaining consent the research team member will ensure the participant is capable of providing legal consent – based on their literacy, ability to understand the study and ensuring they are not influenced by power dynamics. Informed consent will be obtained prior to surgery by a member of the research team. eConsent will be obtained using RedCap if feasible. Paper copies will be kept in the participants medical records, a copy will be given to the participant and one will be stored in a locked file within the department of anaesthetics.
Will participants be consented verbally/explicitly/using eConsent?	eConsent will be used when feasible, alternatively paper based consent forms will be used as noted above.
Will participants be given a specific time period to consider participating?	Yes, participants will be given time in between their visit to the pre-admission and their day of surgery to consider participating and before providing informed consent.
Review of existing databases or databanks (please identify the database/databank and	RedCap will be used to obtain eConsent and collect/transcribe data collected during this study.

the custodian)	
Review of clinic files (please include who will be reviewing these files, for example a research coordinator).	Clinic files will be reviewed by the Clinical Research Coordinator (Department of Anaesthetics) and the principal investigator.
Advertisements (please include where the advertisement will be placed for example, in a newspaper, poster in a clinic or hospital foyer, radio announcements, website etc.)	Currently there is no plan for advertising.
Information Letter to Medical practitioners	No, the treating surgical team will be informed during the recruitment and screening process to ensure they support their patient's involvement.
Explain how potential participants will be screened for the study	Participants will be screened via the surgical lists for JL theatres.
Any other potential recruitment methods.	N/A

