Protocol version	V 1 Dated 16.5.2022
Objectives	
Primary objective	Pilot study to assess the feasibility of a large multicentre randomised trial of perioperative fluvoxamine in the prevention of postoperative delirium
Secondary objectives	
1) Obtain the trial enrolment rate per month2) Reasons for screening failure/enrolment refusal into the trial3) Assess the influence of perioperative fluvoxamine on the rate and severity of delirium on POD1–44) Assess the rate and severity of adverse effects of fluvoxamine5) Examine the number of missed study drug doses due to adverse effects6) Assess the ability to acquire EEG recordings on POD1+27) Differences in EEG slow wave activity (0.5–6Hz) on POD1+2 with perioperative fluvoxamine8) Assess the ability to acquire plasma biomarkers IL-8 and NfL on POD1+29) Group differences in levels of plasma IL-8 and NfL on POD1+210) Assess the fraction of completed 3D-CAM assessments11) Influence of perioperative fluvoxamine on Delirium Rating Scale -Revised 98, 3D-Confusion Assessment Method-S, Richmond Agitation and Sedation Score on POD1–412) Influence of perioperative fluvoxamine on postoperative pain scores13) Influence of fluvoxamine on postoperative change in cognition, disability or depression scores.14) Differences in C-Reactive Protein (CRP), White Cell count (WCC) and troponin.
Study design	Double blind placebo-controlled randomized controlled feasibility trial
Planned sample size	46
Selection criteria	Elective non-cardiac, non-intracranial surgical patients who are older than 60 years old with an expected length of hospital stay of >2 days

Study procedure	Patients will be randomised to: (1) 100 mg fluvoxamine the night before surgery, AM and PM on the day of surgery, and AM and PM on POD1, or (2) placebo control
Statistical considerations	This pilot study is powered for a 25% recruitment rate in approached patients with a 95% confidence interval of 13%.
Duration of the Study	1 year

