3. STUDY OBJECTIVES

3.1. PRIMARY OBJECTIVES:

Assessing the enrolment rate of approached patients in this pilot study to determine the feasibility of a larger trial

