7. OUTCOMES

7.1. DEFINITION OF OUTCOMES

Delirium severity will be defined using the Delirium Rating Scale Revised-98 (DRS-R-98)

Delirium incidence will be defined using the 3D-CAM and administered as described.^{32,33}

Acquisition of EEG recordings and quantification of awake EEG SWA (EEG power 0.5-6 Hz) will proceed as published previously by our group.¹⁴

Blood will be processed with quantitation of IL-8 and NfL as we have previously described.³⁴ At Royal Prince Alfred Hospital patients will have CRP, WCC and troponin sent as SOC.

Rates for enrollment will be calculated with denominators of total eligible and total approached for consent. The rate of screen failures will provide information on the surgical volume and coordinator staff required. A high number of study refusals due to concerns of study drug or type/number of outcome assessments will provide valuable information on revising the study design and/or administration of study procedures for a future investigation. Enrollment rates of <25% based on total approached for consent will warrant revision of study design or additional sites in a future larger scale trial.

Rates of adherence will be computed based on the intake of each dose of study drug, with adherence defined as at least 80% of doses taken (4 of 5 total doses). Reasons for not taking study medication will be classified into the following categories: 1) forgetfulness, 2) misunderstanding, 3) interference with medical care, 4) possible side effects, 5) fear/stress, 6) lack of time.

Rates of data acquisition for CAM assessments, EEG recordings, and IL-8 sampling will be compiled at each time point. Less than 90% collection rate for interpretable outcome measures will constitute a “no go” signal, warranting revision of schedule of activities or pipeline for processing biomarkers.

Adverse events (AE) of nausea, diarrhea, headache, and insomnia will be evaluated from evening before surgery through POD 3. A high rate of AEs directly related to the study drug (>30%) combined with an overall adherence rate of <80% will constitute a “no go” signal for a larger clinical trial.

Postoperative pain scores will be determined using the visual analogue scale (VAS)

Patients at RPAH, will have a thromboelastograph sent prior to start of surgery to monitor platelet function.

Change in cognition and disability at 30 days postoperatively

Blood loss

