8. STATISTICAL CONSIDERATIONS

8.1. SAMPLE SIZE OR POWER CALCULATION

Based on an estimated 25% enrollment rate, then n=184 screen-positive patients will provide sufficient power to measure this proportion with a 95% confidence interval width of 13%. From our preliminary data, we expect successful enrollment of 46 patients across 2 sites over 9 months. This will allow estimation of the proportion of patients who will complete at least 80% of doses of fluvoxamine with a 95% confidence interval width of 23%, assuming a completion rate of 80%.

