9. DATA COLLECTION

9.1. PARTICIPANT REGISTRATION

Participants will be registered/enrolled for the trial at the time of consent and will be provided with a study ID. The participant will be randomised to interventional group or placebo.

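### Section 6.4 says screening logs will not be collected, yet the primary enrolment rate and the screen-failure and refusal outcomes need those counts, and the protocol describes no other source for them

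*Protocol*

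**What the plan says.** The table in Section 6.4 asks what screening data will be collected and whether the data of ineligible patients are kept. The answer describes a check of theatre lists for procedure, age and ASA status, and ends "Screening logs will not be collected".

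Other parts of the protocol depend on counts from screening and approach:

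- **Primary objective (Section 3.1):** "Assessing the enrolment rate of approached patients in this pilot study to determine the feasibility of a larger trial".
- **Denominators (Section 7.1):** "Rates for enrollment will be calculated with denominators of total eligible and total approached for consent".
- **Decision rule (Section 7.1):** "Enrollment rates of <25% based on total approached for consent will warrant revision of study design or additional sites".
- **Secondary objective 2 (synopsis):** "Reasons for screening failure/enrolment refusal into the trial".
- **First feasibility outcome (Section 6.1):** "Incidence and reasons for screen failures and withdrawals". Section 7.1 uses the screen-failure rate to judge the surgical volume and staffing needed.
- **Sample size (Section 8.1):** "n=184 screen-positive patients will provide sufficient power to measure this proportion". The synopsis states the same target for approached patients.

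On who receives a record, Section 9.1 says "Participants will be registered/enrolled for the trial at the time of consent", with a study ID issued then. Section 6.5 places enrolment after both consent and confirmation of eligibility. Paper case report forms carry the ID (Section 9.2).

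**The concern.** This is a feasibility trial, and its main result is a proportion. The numerator is documented because every enrolled patient gets a study ID. The denominator consists mostly of people who never get one, and the only sentence about their records says that logs are not collected.

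Three things are at stake: the primary estimate, the reasons for refusal and screen failure that are meant to guide redesign, and the planning of the next trial. Section 1.2 intends to use the enrolment rates to work out how many eligible and approached patients the later trial will need. An analysis plan cannot repair this, because it cannot supply data that were not recorded. Counts and reasons for refusal are also hard to reconstruct reliably afterwards.

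**Working it through.** **Inputs.** Section 8.1 gives an expected enrolment rate of 25%, n = 184, 46 enrolled and a 95% confidence interval width of 13%. Section 7.1 gives the threshold: below 25% of those approached.

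**1. The plan's own figure.** 184 × 0.25 = 46. The exact (Clopper-Pearson) 95% interval for 46/184 runs from 18.9% to 31.9%, a width of 13.0 percentage points. The simple normal interval has width 2 × 1.96 × √(0.25 × 0.75 / 184) = 12.5 points. The stated 13% agrees with the exact interval, so the sample-size arithmetic is sound.

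**2. What has to be counted, and where it is recorded.**

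| Quantity | Needed for | Source described |
|---|---|---|
| Enrolled | numerator | study ID, case report form, REDCap |
| Approached | primary rate, 25% rule | none |
| Declined, with reason | secondary objective 2, Section 7.1 | none |
| Eligible | second enrolment rate in Section 7.1 | none; Section 6.4 says no log |
| Screened out, with reason | Sections 6.1 and 7.1, synopsis | none; Section 6.4 says no log |

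On the planned figures, 184 − 46 = 138 patients belong in the denominator without a described record. Contact is also in two stages (Section 6.4): first a member of the anaesthetic department in the pre-admission clinic, then the anaesthetic doctor or the research team. A refusal at the first stage might never reach the research team.

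**3. Effect of incomplete recording.** Let E be the number enrolled, R the number approached but not enrolled, and m the share of R that goes unrecorded. The observed rate is E / (E + (1 − m)R). Since E is complete, any loss from R raises the rate.

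With E = 46 and R = 138 (true rate 25.0%) and assumed values of m:

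- m = 10%: 46 / (46 + 124.2) = 27.0%
- m = 20%: 46 / (46 + 110.4) = 29.4%
- m = 30%: 46 / (46 + 96.6) = 32.3%

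**4. Loss needed for a rate below the threshold to read as 25%.** With E = 46, an observed 25% requires 138 recorded non-enrolled patients, so m = 1 − 138/R.

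- True 24%: 46/0.24 = 191.7 approached, R = 145.7, m = 5.3%
- True 22%: 46/0.22 = 209.1 approached, R = 163.1, m = 15.4%
- True 20%: 46/0.20 = 230 approached, R = 184, m = 25.0%

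The documents give no value for m. These figures show sensitivity and are not forecasts.

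**The case against.** The strongest reply is that the sentence is narrow. It answers a template question about screening data, including the data of ineligible patients, and follows directly on the theatre-list check. It may mean only that this pre-consent list is not retained. Approach comes later, a simple tally could count it, and Section 7.1 plainly intends the rates to be calculated. The case report form is an attachment that is not shown (Sections 9.3 and 17). The Section 6.4 table refers to particular theatres, and Section 4.5 names only the Sydney hospital, so the table may not describe the US site.

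Much of this stands. A reader might infer that the primary rate cannot be computed at all, or that only consenting patients are recorded. The documents do not go that far: a separate tally of approached patients would give the approached-based rate, and nothing rules one out. What can be said is that none is described. Even on the narrow reading, the eligible count and the screen-failure outcomes lose their source.

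A reader might also infer that the 25% rule passes or fails according to which denominator is chosen. That is not supported. Section 7.1 ties the rule to patients approached for consent, and the per-eligible rate is a second, planned summary. Moreover, if 46 are enrolled from 184 eligible and fewer than 184 are approached, the approached-based rate is above 25%, so that mismatch alone does not trigger the rule.

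**Conclusion.** The contradiction is real and should be resolved before recruitment. Section 6.4 declines to keep the record that Sections 3.1, 6.1 and 7.1 and the synopsis rely on. Followed as written, the eligible-based rate and the screen-failure outcomes have no data source. The approached-based primary rate and the refusal reasons have none described.

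The planned result lies exactly on the threshold, so modest under-recording matters: about 5%, 15% or 25% of refusals missing would lift a true 24%, 22% or 20% to 25%. These shares are assumptions, and the calculation takes the 46 enrolled as fully counted.

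Two wording conflicts are secondary. Section 8.1 attaches the 184 to screen-positive patients, while the synopsis and the Section 7.1 rule use approached patients. Section 9.1 enrols at consent, while Section 6.5 also requires confirmed eligibility. The second conflict could affect the numerator, because consent and the cognitive screen fall at the same visit (Section 6.2.1) and Section 6.4 excludes patients who show cognitive dysfunction. No change in the 25% decision has been shown from either conflict.

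**What to change.** 1. In Section 6.4, replace the sentence with a commitment to a prospective, de-identified screening and approach log at both sites, subject to ethics approval. It should record: screened; eligible, with the reason if not; approached; declined, with the reason; consented; enrolled. It should start at first contact in the pre-admission clinic, so that early refusals are counted.
2. In Section 8.1, describe the 184 as patients approached, to match the synopsis and the Section 7.1 rule.
3. Align Section 9.1 with Section 6.5, so that enrolled means consented and confirmed eligible. The endpoint need not be redefined on randomised patients.

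The cost is a protocol amendment, a short form at each site and modest coordinator time. No patients are added, and the sample-size figures stay as they are: 46/184 = 25%, exact 95% interval 18.9% to 31.9%, width 13%.

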6.5. PARTICIPANT ENROLMENT

Participants will be enrolled into the study after the informed consent process has been completed and the participant has been assessed to meet all the inclusion criteria and none of the exclusion criteria. Study participants will receive a study enrolment number and this will be documented in the participant's medical (or personal) record and on all study documents.

During patient enrolment a member of the study team will discuss this with the treating team, anaesthetic doctor and post-operative ward staff. If any issues are raised during this time, they will be referred to the PI for ongoing discussion.

